8.4.2 Secondary objectives analysis

Acute (30 days post procedure)

- Safety
The percentage of subjects with peri-procedural events within 30 days post procedure will be computed as follows:

$$\frac{\text{Number of subjects with peri procedural events within 30 days post procedure}}{\text{Number of subjects that underwent the procedure}} * 100$$

- Performance
The mean reduction in office Systolic and Diastolic Blood Pressure at 1 month and the mean reduction in ambulatory Systolic and Diastolic Blood Pressure at 1 month will be calculated in a similar way as described for the primary objective (Section 8.4.1). The percentage of subjects achieving office Systolic Blood Pressure < 140 mmHg at 1 month will be computed as follows:

$$\frac{\text{Number of subjects achieving office SBP < 140 at 1 month}}{\text{Number of subjects with data available at 1 month}} * 100$$

Mid to long term (6 and 12 months)

- Safety
Renal function change based on eGFR will be summarized by:
 1. Computing the change of the eGFR at 6 and 12 months, compared to baseline for each patient with data available at both time points.
 2. Calculating the mean and standard deviation of the eGFR change at those intervals

Assessment of renovascular safety as measured by occurrence of new renal artery stenosis (> 50%) and aneurysm at the site of ablation per Renal Artery Imaging will be summarized at 6 months as a percentage of subjects who have stenosis (> 50%) or aneurysm.
- Performance

The mean reduction in office Systolic Blood Pressure at 12 months, the mean reduction in office Diastolic Blood Pressure at 6 and 12 months and the mean reduction in ambulatory Systolic and Diastolic Blood Pressure at 6 and 12 months post denervation will be calculated in a similar way as described for the primary objective (Section 8.4.1).

Percentage of subjects achieving office Systolic Blood Pressure < 140 mmHg at 6 and at 12 month will be computed as follows:

$$\frac{\text{Number of subjects achieving office SBP} < 140 \text{ at 6 months}}{\text{Number of subjects with data available at 6 months}} * 100$$

$$\frac{\text{Number of subjects achieving office SBP} < 140 \text{ at 12 months}}{\text{Number of subjects with data available at 12 months}} * 100$$

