- Subject has active systemic infection
- Subject has known renal arteries with diameter(s) < 4 mm
- Subject has an estimated GFR < 45 mL/min per 1.73 m² using the MDRD formula
- Subject had a renal transplant or is awaiting a renal transplant

Procedural Exclusions:

Subjects who have been enrolled in the study, and in whom the procedure was started, but do not have the EnligHTN™ Renal Denervation System enter their body, due to their anatomy, circumstances related to the procedure, or physician judgment will be classified as procedurally excluded. These subjects will be followed for 30 days post procedure. The reason for the procedural exclusion will be documented on the Procedural CRF.

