4.8 Number of Subjects required to be included in the Investigation

Enough subjects will be enrolled to have approximately 500 subjects undergo the renal denervation procedure in the investigation. Procedurally excluded subjects will not count towards the expected number of treated subjects.

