4.10 Devices Used

The EnligHTN™ Renal Denervation System is designed to deliver radiofrequency (RF) energy to the renal nerves to achieve targeted denervation. The system consists of the EnligHTN™ RF Ablation Generator (generator), the EnligHTN™ Renal Artery Ablation Catheter (ablation catheter), and the EnligHTN™ Guiding Catheter (optional).

The manufacturer of the EnligHTN™ Renal Denervation System is St. Jude Medical, Cardiovascular Division, [name]

The following market approved St. Jude Medical devices to be initially used in this investigation are:

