8.3 Analysis Population

All patients who have signed a Patient Informed Consent (PIC) will be considered enrolled in the study. However, Primary Analysis population will include those patients that have signed a PIC form, and had the EnligHTN™ Renal Denervation System enter his/her body. The sample size of 500 subjects refers to those subjects in the Primary Analysis population.

As Treated population will include all subjects in whom renal denervation was performed in a minimum of one renal artery per kidney (according to the Instructions for Use).

It is anticipated that there may be subjects who have been enrolled in the study but are not included in the Primary Analysis population or As Treated population, such as:

- Subjects who are enrolled but do not meet baseline inclusion or exclusion criteria before the procedure; these are considered the screen failure population.
- Procedurally excluded populations will include subjects who have enrolled in the study and start the procedure, but do not have the EnligHTN™ Renal Denervation System enter his/her body, due to their anatomy, circumstances related to the procedure, or physician judgment.

Subjects who withdraw from the investigation will not be replaced in any analysis population.

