8.4 Data Analysis and Reporting

Data analysis will be performed across all subjects, based on Primary Analysis population unless otherwise specified.

The data collected will be presented using the appropriate summary statistics. Continuous data will be summarized using descriptive statistics (number of observations, mean, standard deviation, minimum and maximum values).

Continuous primary and secondary outcomes between time points will be compared as follows: normality of data will be verified with the use of box plots and Kolmogorov-Smirnov normality tests. For normally distributed data, comparisons will be performed using paired t-tests. In cases

CV-12-064-EU-HT_CIP_V2.0_final_25Mar2014 EnligHTN European Observational Study

©2014 – SJM International, Inc.: All rights reserved. No portion of this work may be reproduced in whole or in part without the express written permission of SJM International, Inc.

where the data is not normally distributed, the non parametric Wilcoxon-Signed-Rank test will be used to analyze the data. Results will be expressed in terms of p-values. Categorical data will be summarized using frequencies and percentages.

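### The 30-day peri-procedural safety percentage has an undefined denominator and appears to leave out subjects whose procedure was started but who were procedurally excluded

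*Combined protocol and SAP*

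**What the plan says.** Section 8.4.2 (Acute, Safety) defines the 30-day percentage as "Number of subjects with peri procedural events within 30 days post procedure" over "Number of subjects that underwent the procedure", times 100. Neither part names an analysis population, and the plan does not define what it means to have undergone the procedure.

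The other relevant statements are these:

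- Section 8.4 sets the default: "Data analysis will be performed across all subjects, based on Primary Analysis population unless otherwise specified".
- Section 8.3 defines that default: "Primary Analysis population will include those patients that have signed a PIC form, and had the EnligHTN™ Renal Denervation System enter his/her body".
- Section 8.3 also says that some subjects may be "enrolled in the study but are not included in the Primary Analysis population or As Treated population, such as" screen failures and the procedurally excluded.
- Section 4.5 describes the procedurally excluded as enrolled subjects whose procedure was started but in whom the system did not enter the body. The reasons are anatomy, "circumstances related to the procedure, or physician judgment will be classified as procedurally excluded. These subjects will be followed for 30 days post procedure".
- Section 4.8 plans for about 500 subjects to undergo renal denervation and adds: "Procedurally excluded subjects will not count towards the expected number of treated subjects".
- Section 6.7.8 applies safety surveillance to all enrolled subjects. It treats an adverse event as procedure related if it happened during the procedure, or is directly linked to it, without being directly caused by the device.

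**The concern.** The acute safety objective in 4.2 concerns peri-procedural events up to 30 days. Procedurally excluded subjects have had a procedure started and are followed for exactly that window, yet no analysis in 8.4.1 to 8.4.3 is written to use their follow-up.

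The omission may not be neutral. One reason for stopping a case is circumstances arising from the procedure. A bleed at vascular access, or an injury from another maker's guiding catheter, could stop the case before any EnligHTN component is in the body. By 6.7.8 that is a procedure-related event, but the subject becomes procedurally excluded and, under the default population, leaves the percentage. The event itself can then decide whether the subject is counted, which is selection on the outcome.

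Separately, a denominator that can be read in more than one way leaves a reported safety figure to whoever programs it.

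**Working it through.** **Which subjects are counted.** The plan states no value for this percentage, so there is no figure to reproduce. The first check is textual.

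1. Section 8.4 applies the Primary Analysis population unless something else is specified.
2. The formula in 8.4.2 names no other population. Its denominator phrase could be a specification, but it is undefined.
3. The closest use of the phrase is in 4.8, where those who undergo renal denervation are the roughly 500 treated subjects, and the procedurally excluded do not count towards them.
4. Section 8.3 places the procedurally excluded outside both analysis populations.

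The most natural reading therefore leaves these subjects out of numerator and denominator. Two other readings remain open: counting every started procedure, or counting their events in the numerator only.

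**How much it could matter.** Inputs:

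- N = 500, the size that 8.3 gives to the Primary Analysis population. The sample size in 8.2 reproduces: (1.96 × 24.7 / 2.35)² = 424.4, rounded up to 425, and 425 / 0.85 = 500. Nothing here changes it.
- k = procedurally excluded subjects: 5, 10 or 25 (assumed).
- p = event rate in the Primary Analysis population: 2% or 5% (assumed).
- q = event rate among the procedurally excluded: 0% to 40% (assumed).

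Percentage with these subjects left out: p.

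Percentage with them in both parts: (500p + kq) / (500 + k).

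Shift: k(q − p) / (500 + k).

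| k | Left out (p) | q = 0% | q = 10% | q = 20% | q = 40% |
|---|---|---|---|---|---|
| 5 | 2.00% | 1.98% | 2.08% | 2.18% | 2.38% |
| 5 | 5.00% | 4.95% | 5.05% | 5.15% | 5.35% |
| 10 | 2.00% | 1.96% | 2.16% | 2.35% | 2.75% |
| 10 | 5.00% | 4.90% | 5.10% | 5.29% | 5.69% |
| 25 | 2.00% | 1.90% | 2.38% | 2.86% | 3.81% |
| 25 | 5.00% | 4.76% | 5.24% | 5.71% | 6.67% |

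The extremes are:

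- k = 25, p = 5%, q = 0%: 25 / 525 = 4.76%, a shift of -0.24 points.
- k = 25, p = 2%, q = 40%: (10 + 10) / 525 = 3.81%, a shift of +1.81 points.

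The percentage rises only when q exceeds p.

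The numerator-only reading gives (500p + kq) / 500. For k = 25, p = 2%, q = 40% this is 20 / 500 = 4.00%. In that case the same data give 2.00%, 3.81% or 4.00%, depending only on how the formula is read.

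**The case against.** The strongest reply is that the exclusion is inferred. The default in 8.4 yields to anything otherwise specified, and an explicit denominator may be such a specification. Section 4.5 says the procedure was started in these subjects and times their follow-up from it, so a literal reader could count them as having undergone it. Section 4.8 is a recruitment rule, not an analysis rule. This stands as a limit on certainty: the plan appears to exclude them, and does not say so outright. It also strengthens the case for defining the term.

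Four stronger conclusions are tempting, and the documents do not support them:

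- **That the percentage is biased downward.** No count of procedurally excluded subjects and no event rate is given. If these subjects have fewer events than the others, counting them lowers the percentage.
- **That complications of aborted cases vanish from the safety record.** Section 6.7.8 requires serious adverse events and adverse device effects to be reported for every enrolled subject, and 13.1 has the sponsor review the investigator's assessments. The gap is in one planned summary.
- **That this is the only planned safety percentage.** Section 8.4.2 also plans the 6-month percentage with new renal artery stenosis or aneurysm.
- **That the brand of guiding catheter decides who is in the Primary Analysis population.** Section 4.10 lists the optional EnligHTN guide as part of the system, so on one reading a case stopped after that guide is in, while the same case with another maker's guide is out. But the listed system also includes the generator, which never enters the body, so the entry wording cannot be literal. It may mean any component or the ablation catheter; brand dependence follows only from the first.

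**Conclusion.** The concern holds in a limited form. As written, the plan most naturally leaves procedurally excluded subjects out of the 30-day percentage, and it leaves the denominator undefined. Because a complication before any EnligHTN component enters the body can cause the exclusion, downward bias is possible. It is not shown.

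The range of about -0.2 to +1.8 percentage points rests wholly on assumed counts and rates. With 5 such subjects the shift is at most about 0.4 points (2.00% to 2.38%). The upper end needs 25 subjects with a 40% event rate against 2% in the others. The primary endpoint and the sample size are unaffected.

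This should be corrected because the subjects are already followed for the right window and the remedy is a matter of wording.

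**What to change.** In 8.4.2, define the 30-day peri-procedural percentage over all enrolled subjects in whom the procedure was started, including the procedurally excluded, and use that same group in numerator and denominator. Beside it, report the percentage in the Primary Analysis population, and list the number of procedurally excluded subjects and their events.

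Leave the Primary Analysis population definition as it is. Tying entry to the ablation catheter might seem to settle the guiding-catheter question, but if entry now means any component, it would move subjects exposed only to the EnligHTN guide, a listed study device, out of the device population. It would also alter the population for the primary endpoint.

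The cost is a wording change and a little more reporting. The 30-day follow-up and the CRF entry for the reason for exclusion already exist in 4.5, so no new data collection is needed. The stated safety percentage may turn out less favourable.

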8.4.1 Primary objective analysis

The mean reduction of office SBP at six (6) months of the study will be analyzed by:

1. Computing the reduction of SBP measurements at 6 months compared to baseline for each patient with data available in both time points.
2. Calculating the mean and standard deviation of the SBP reduction at 6 months

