8.4.3 Other Analyses

Summary statistics for medications being used by subjects and changes to them will be presented for each follow-up visit.

In addition, subgroup analyses may be performed as needed, e.g.:

- for subjects that have the renal denervation procedure performed on one side but not the other (due to their anatomy, circumstances related to the procedure, or physician judgment)
- based on the number of ablation points performed
- by the subject's primary disease conditions.

Ad hoc analyses may be performed as needed. Analysis may be performed based on As Treated population as deemed appropriate. In general, data analysis will be performed on a per subject basis. But the data analysis may be presented per kidney, or on renal artery basis, as appropriate.

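### Does the 6-month renal artery stenosis or aneurysm percentage need a written denominator, given that imaging is optional?

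*Combined protocol and SAP*

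**What the plan says.** The 6-month renovascular endpoint in Section 8.4.2 is the "occurrence of new renal artery stenosis (> 50%) and aneurysm at the site of ablation per Renal Artery Imaging", and it "will be summarized at 6 months as a percentage of subjects who have stenosis (> 50%) or aneurysm". No formula follows. The same section does give formulas for four other percentages: 30-day peri-procedural events, divided by the subjects who had the procedure, and office SBP below 140 mmHg at 1, 6 and 12 months, each divided by the subjects with data at that visit.

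The 6-month image is not mandatory. Section 5.4.6 collects it where it exists, and footnote 1 of Table 1 ties it to clinical routine.

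Three general rules bear on the denominator:

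- **Population.** Section 8.4: "Data analysis will be performed across all subjects, based on Primary Analysis population unless otherwise specified". Section 8.3: "The sample size of 500 subjects refers to those subjects in the Primary Analysis population".
- **Presentation.** Section 8.4: "Categorical data will be summarized using frequencies and percentages". The number of observations is listed for continuous data only.
- **Available data.** Section 8.4.1 computes the SBP reduction "for each patient with data available in both time points". Section 8.4.2 carries this over to the other blood pressure changes and uses an equivalent rule for eGFR.

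Section 8.3 also defines the As Treated population as "all subjects in whom renal denervation was performed in a minimum of one renal artery per kidney". Section 8.4.3 foresees subjects with the "renal denervation procedure performed on one side but not the other".

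**The concern.** This is the only 6-month endpoint that looks for arterial damage on imaging, and the only percentage in Section 8.4.2 without a written denominator. If the default in Section 8.4 is read as a denominator, it gives about 500. Every subject without an image would then enter the calculation as a non-event, and the rate would be diluted in proportion to the share not imaged. If the denominator is the imaged subjects, the same images give a higher rate. A reader could not tell which had been done if the report showed only a percentage.

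The default population adds a smaller difficulty. It takes in anyone whose body the system entered, ablated or not, while the event must lie at an ablation site. The As Treated set does not solve this, because it drops subjects treated on one side only.

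**Working it through.** **Inputs.** From Section 8.2: SD 24.7 mmHg, half-width 2.35 mmHg, two-sided 95%, 425 evaluable, 15% attrition, about 500 in total. The plan states no figure for the renovascular percentage. It gives neither an imaging share nor an expected event count, so the two events and the shares below 85% used here are assumptions.

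**The plan's own figure.** n = (1.96 × 24.7 / 2.35)² = 424.4, rounded up to 425; 425 / 0.85 = 500. Both reproduce. If the 15% attrition has all occurred by 6 months, at most 500 × 0.85 = 425 subjects can have a 6-month image.

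**Size of the difference.** Rate over 500 = rate among imaged × (number imaged / 500). With two events and exact (Clopper-Pearson) 95% limits:

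| Denominator | Basis | Factor | Rate | 95% CI |
|---|---|---|---|---|
| 500 | whole population | – | 0.40% | 0.05 to 1.44% |
| 425 | plan's attrition | 0.85 | 0.47% | 0.06 to 1.69% |
| 250 | assumed share | 0.50 | 0.80% | 0.10 to 2.86% |
| 125 | assumed share | 0.25 | 1.60% | 0.19 to 5.66% |

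With no events, the upper limit is 1 − 0.025^(1/n): 0.74% on 500, 0.86% on 425, 1.46% on 250 and 2.91% on 125.

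**Which reading the text supports.**

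1. The default in Section 8.4 names the set of subjects to be analysed. It is not a rule for missing data. The SBP below 140 mmHg percentages are calculated within that same population, yet they divide by subjects with data.
2. Ambulatory blood pressure is the closest parallel. Table 1 makes it optional under the same footnote as the 6-month image, and Section 8.4.2 analyses it as in Section 8.4.1, that is, in subjects with both values. The plan therefore already handles one optional assessment by leaving out those who lack it.
3. The one percentage that divides by everyone who had the procedure is the 30-day event rate. Under Section 6.7.8, safety surveillance covers all enrolled subjects, so that denominator is also the group observed for the outcome.
4. The endpoint is defined by imaging. A subject without an image has no value for it, and no section says that such a subject counts as event-free.

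**What the reader would see.** Categorical results are to be shown as counts and percentages. With at least one event, the two together give the denominator up to rounding: 2 events at 0.8% imply 2 / 0.008 = 250. With no events it cannot be recovered.

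**The case for a change.** The strongest case for a change is that the plan wrote out an available-data denominator where it wanted one and did not do so here, while the neighbouring safety percentage divides by all treated subjects. Zero events is a plausible result: Section 3 reports no new stenoses during the procedure in the feasibility study. In that case the count and percentage do not reveal the denominator, and the upper limit could be 0.74% or 2.91% depending on how many were imaged. Section 9 says that the data may support a market-approval application. One formula would settle the matter before results are known.

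Part of this stands. The wording does not expressly exclude 500, and a report of no events without the number imaged would be hard to interpret. But the silence does not instruct anyone to count unimaged subjects as event-free, and the other 6- and 12-month analyses point the other way.

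The further additions do not correct a wrong result either. Sections 8.4.1 and 8.4.2 set out no confidence interval for any endpoint, so an exact interval here would be a separate request. A set requiring ablation in at least one artery would be a new population, and the documents do not say how many subjects it would remove. Restricting to imaged subjects also leaves a group selected by local routine. That may bias the rate in a direction the documents do not determine, and a written formula would not cure it.

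**Conclusion.** The omission is real but is a gap that analysts fill sensibly; no change to the plan is needed. The natural denominator is subjects with an evaluable 6-month image. It follows from the imaging-based definition and from the treatment of the other 6- and 12-month outcomes.

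At the plan's own attrition, the choice moves an assumed two-event rate from 0.40% to 0.47%. Larger differences, up to a factor of four at 125 imaged (500 / 125), rest on imaging shares that the documents do not give. The endpoint is secondary, single-arm and descriptive, with no hypothesis, threshold or stopping rule attached. Recognised renal artery complications also reach the sponsor through Section 6.7.8, which requires all serious adverse events and all adverse device effects to be reported. That does not replace imaging, but it limits what hangs on this one percentage.

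The conclusion assumes that the analyst follows the section's own pattern. A report that gave the number imaged out of the number treated would remove the remaining doubt, including when no events are found.

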8.4.3 Other Analyses

Summary statistics for medications being used by subjects and changes to them will be presented for each follow-up visit.

In addition, subgroup analyses may be performed as needed, e.g.:

- for subjects that have the renal denervation procedure performed on one side but not the other (due to their anatomy, circumstances related to the procedure, or physician judgment)
- based on the number of ablation points performed
- by the subject's primary disease conditions.

Ad hoc analyses may be performed as needed. Analysis may be performed based on As Treated population as deemed appropriate. In general, data analysis will be performed on a per subject basis. But the data analysis may be presented per kidney, or on renal artery basis, as appropriate.

